3.2 Rationale of study design

A randomized, placebo-controlled, partial-blind approach is used to eliminate potential bias in reporting safety and biological activity data in this study. The study will be blinded to patients, investigator site staff and the clinical trial team at the time of randomization. Unblinding of patients as they reach the end of double-blind treatment period is planned. This together with the effect of VAY736 on certain assessments may lead to members of the clinical trial team becoming inadvertently unblinded towards the end of the study period.

In addition, the study includes a staggered enrollment to allow progression between the 3 mg/kg and 10 mg/kg to be dependent upon a safety review milestone. The initial 9 patients dosed prior to the safety review will include only the 3 mg/kg VAY736 (n=6) dose and placebo patients (n=3). The rationale for this lower dose group is to confirm that the safety profile in patients with PV with regard to infusion reactions and other short term safety parameters (e.g. chemistry and hematology) is favorable, similar to that observed in study CVAY736X2101. A favorable safety review by the DMC will then enable randomization to commence into the 10 mg/kg dose group and completion of the remaining 3 mg/kg and placebo groups.

In the event that efficacy is observed with both 3 mg/kg and 10 mg/kg, the relationship between dose and parameters of clinical response (e.g., time to remission, duration of remission) can be better explored with a range of doses and exposures offered by these two dose groups.

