5.2 Treatment arms

Patients will be randomized to one of the following 3 treatment arms, defined as:

- VAY736 active: single i.v. dose of 3 mg/kg VAY736 from infusion bag containing the active compound on Day 1
- VAY736 active: single i.v. dose of 10 mg/kg VAY736 from infusion bag containing the active compound on Day 1
- VAY736 placebo: single i.v. dose from infusion bag without active compound on Day 1

The overall randomization ratio will be 3:3:2. Before the first IA and safety review 9 patients will be randomized to the above treatments in a ratio of 2:0:1. After the safety review the remaining patients will be randomized in a ratio of 1:3:1.

Open label

Patients entering the open label cohort will be assigned to receive

- VAY736 active: single i.v. dose of 3 mg/kg VAY736 from infusion bag containing the active compound on Day 1 if blind is broken prior to the completion of the safety review
- VAY736 active: single i.v. dose of 10 mg/kg VAY736 from infusion bag containing the active compound on Day 1 if blind is broken after the completion of the safety review

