5.5.7 Recommended treatment of adverse events

Potential adverse events should be treated symptomatically.

Intravenous administration of mAbs can be associated with infusion reactions secondary to hypersensitivity, Commercially Confidential Information. Most infusion reactions occur within the first 2 hours of mAb exposure. In this study, VAY736 will be infused over a 2 hour period. During this period, administration of VAY736 can be modified and clinical treatment provided as determined by the treating physician on a case-by-case basis. The following guidelines are provided using the National Cancer Institute Common Toxicity Criteria for allergic reaction, anaphylaxis and cytokine release [NCI-CTCAE/v4.03, Reference <http://evs.nci.nih.gov/ftp1/CTCAE/About.html>].

In the case of a suspected infusion reaction, the infusion can be stopped for 30 minutes and the patient observed to determine the severity of the reaction. Depending on the assessment of the patient, medication can be administered and the infusion can be restarted at a reduced rate if necessary. Additional guidance on severity grading and treatment includes the following:

- Mild National Cancer Institute (NCI) grade 1 infusion reactions do not require treatment.
- In case of moderate NCI grade 2 infusion reactions requiring symptomatic treatment, the patient can be treated with anti-histamines, NSAIDs, paracetamol/acetaminophen, intravenous fluids) as determined by the investigator, but only while adhering strictly to the maximal daily dose limits of these medications. The infusion can be stopped for 15 minutes and then restarted at a reduced rate.
- In case of more severe NCI grade 3 or 4 reactions, the infusion should be stopped and corticosteroids according to local guidelines administered intravenously.
- Other available medications at the bedside should include paracetamol/acetaminophen, adrenaline, bronchodilators, and /intravenous preparations of anti-histamines.

Infusion reactions of severity NCI grade ≥ 2 despite pre-medication with paracetamol/acetaminophen and an H1 blocker may require modification of the pre-treatment regimen. Medication to prevent or treat the signs and symptoms of infusion-related reactions will be provided by the study site.

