5.5.11 Discontinuation of study treatment and premature subject withdrawal

Study “Stopping rules”

Commercially Confidential Information

However, infusion reactions (hypersensitivity, cytokine release, anaphylaxis) can occur with administration of biologics,

Commercially Confidential Information . Increased susceptibility to infection is also a potential risk with therapies targeting elements of the immune response. Thus for patients on active treatment, the following guidance and stopping rules are provided:

Dose limiting toxicities (DLTs) will be assessed according to the standardized toxicity grading scale, the NCI Common Toxicity Criteria for Adverse Events [NCI-CTCAE/v4.0, Reference <http://evs.nci.nih.gov/ftp1/CTCAE/About.html>]. Although the stopping criteria will not incorporate an absolute requirement for causality, the potential relationship between an adverse event and VAY736 will be evaluated carefully on a case-by-case basis.

Overall study:

The study will be stopped if any of the following criteria are met, and no further patient will be dosed pending a full safety review:

- Any treatment-related death
- Decrease in neutrophil count:
 - a. If any subject requires G-CSF or GM-CSF treatment for neutropenia, or
 - b. If two or more subjects manifest a persistent neutrophil count <500 cells/uL, or
 - c. If four or more subjects manifest a persistent neutrophil count <1000 cells/uL
- More than 1 infusion reaction of grade 3 severity of the NCI-CTCAE/v4.0 Criteria within the first 5 treated subjects and an incidence of >20% thereafter
- Any treatment-related, grade 3 toxicity of the NCI-CTCAE/v4.0 Criteria with the following exceptions:
 - Events of Special Interest, including infusion-related (hypersensitivity, cytokine release, anaphylaxis), decreased neutrophil or leukocyte counts not requiring treatment, and diagnostic procedures involving elective or non-urgent hospital admission
 - Disease Specific Events that are due to the patients underlying PV diagnosis
 - AE/SAEs unrelated to the experimental compound as assessed by the investigator or Novartis
- Clinically significant (according to the investigator) and study drug-related, persisting changes from baseline in vital signs, electrocardiograms, or medically relevant, persistent changes in laboratory parameters, which are not consistent with existing co-morbidities, in >1 patient within the first 5 treated subjects and an incidence of >20% thereafter

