8.4 Safety Data Review Committee

An internal Safety Data Monitoring Committee (DMC) will be established to review safety data in an unblinded fashion throughout the conduct of the study. Specific details of the composition and scope of its mandate will be presented in a DMC charter document. The committee will be comprised of study-independent physician(s), clinical researchers and a statistician. The DMC members will be separate from the pre-clinical and clinical teams involved in the VAY736 program. Full details of the committee's mandate will be provided in the team charter, but at a minimum the Safety DMC will make recommendations concerning study continuation and/or material changes in the risk/benefit profile of VAY736 in PV patients to the study team. The Safety DMC will review all safety data available to the 9th patient achieving Week 6, the "safety review" milestone of the study design. The Safety DMC will review all safety data available after the 14th patient completes week 12 (this review will include data from patients on 10 mg/kg VAY736). The Safety DMC will also review every documented SUSAR.

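### Protocol 5.5.11: the infusion-reaction stopping rule is misworded; taken literally it cannot be met by 10 mg/kg reactions alone and leaves out non-fatal grade 4 reactions

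*Protocol*

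**What the plan says.** Protocol 5.5.11, under the overall-study stopping rules, stops dosing pending a full safety review when any one bullet is met. Four parts of that list matter here.

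- The infusion-reaction bullet: "More than 1 infusion reaction of grade 3 severity of the NCI-CTCAE/v4.0 Criteria within the first 5 treated subjects and an incidence of >20% thereafter".
- The general toxicity bullet: "Any treatment-related, grade 3 toxicity of the NCI-CTCAE/v4.0 Criteria with the following exceptions". Its first exception is "Events of Special Interest, including infusion-related (hypersensitivity, cytokine release, anaphylaxis"), so infusion reactions are left to their own bullet.
- The vital-sign, ECG and laboratory bullet, which uses the same construction: "in >1 patient within the first 5 treated subjects and an incidence of >20% thereafter".
- A treatment-related death has its own bullet. The list ends with a clause on changes that the investigator or sponsor considers unsafe.

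Protocol 5.2 sets the dosing order: "Before the first IA and safety review 9 patients will be randomized to the above treatments in a ratio of 2:0:1" (3 mg/kg, 10 mg/kg, placebo). Section 3.2 confirms that 10 mg/kg starts only after a favorable review.

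Protocol 5.5.7, on managing the individual patient, names both grades: "In case of more severe NCI grade 3 or 4 reactions, the infusion should be stopped".

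Under Protocol 8.4 the DMC will "review safety data in an unblinded fashion throughout the conduct of the study". The SAP sets no stopping limit in its visible text.

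**The concern.** The list works by 'any of', but inside the infusion-reaction bullet the two limits are joined by 'and'. Followed as written, a later incidence above 20% counts only if the first five subjects have already produced more than one reaction. Those five are on 3 mg/kg or placebo. The 10 mg/kg dose is the one with no prior exposure in this population when it starts, and its reactions cannot meet the bullet by themselves.

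The grade wording leaves a second gap. A bullet limited to grade 3 does not literally include grade 4, and the general bullet does not pick it up because infusion-related events are exempt.

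A mandatory rule should give sites, ethics committees and the DMC the same answer from its words. Here two readings disagree on whether dosing must stop, in the only visible numeric limit on infusion reactions at 10 mg/kg.

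**Working it through.** The protocol states no operating characteristics for this rule, so there is no figure to reproduce. The check tests the logic on the planned dosing order and then adds an illustration.

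**Inputs from the documents.** There are 9 patients at 3 mg/kg, 9 at 10 mg/kg and 6 on placebo (3.1). Six of the 3 mg/kg patients are dosed before the review. After it come the other three, mixed at random with the nine at 10 mg/kg (5.2). That gives 18 patients on VAY736: positions 1 to 6 at 3 mg/kg and positions 7 to 18 mixed. Optional open-label dosing is left out.

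**Step 1: literal rule, no rates needed.** Suppose 0 or 1 of the first five react and all nine at 10 mg/kg react. Of the 13 VAY736 patients after the fifth, 9/13 = 69% react. The second half holds, the first does not, and the bullet is not met. With 'or' it is met.

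**Step 2: early reactions alone.** Suppose 2 of the first five react. If 'thereafter' counts later subjects only, the bullet is not met until later subjects also react. If the count is cumulative, it is met one patient late, at 2/6 = 33%. The text does not say which applies. The two limits are in fact one threshold: 1/5 = 20% does not exceed 20% and 2/5 = 40% does. That points to a continuing limit, not a double condition.

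**Step 3: grade 4.** A non-fatal grade 4 infusion reaction is not named in the infusion bullet, is exempt from the general bullet, and is not a death. It literally meets none of the three.

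**Step 4: corrected rule, no reactions at 3 mg/kg.** Take the corrected rule as at least 2 of the first 5, or a cumulative count k/n > 0.20 from the 6th VAY736 patient on. Since k/n > 1/5 means n < 5k:

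- k = 1: needs n < 5, so it is never met.
- k = 2: both must occur by the 9th patient. C(3,2) = 3 of C(12,2) = 66 orders.
- k = 3: all three by the 14th patient, C(8,3) = 56 orders, or two by the 9th and the third after the 14th, C(3,2) × 4 = 12 orders. Together 68 of C(12,3) = 220, or 31%.
- k = 4 or more: always met, since 4/18 = 22%.

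If placebo patients were counted as treated, 5 or more would always meet it (5/24 = 21%).

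**Step 5: illustration with assumed rates.** The documents give no severe-reaction rate, so every rate here is an assumption. The corrected rule was computed exactly, patient by patient, averaging over the random order of positions 7 to 18. With a cumulative count the literal rule equals P(at least 2 of the first 5), because 2/6 already exceeds 20%. At 5% this is 1 − 0.95^5 − 5 × 0.05 × 0.95^4 = 1 − 0.7738 − 0.2036 = 0.0226. With a later-only count it is lower still.

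| Assumed rate, 3 mg/kg | Assumed rate, 10 mg/kg | Corrected rule | Literal rule |
|---|---|---|---|
| 5% | 10% | 14% | at most 2% |
| 5% | 20% | 30% | at most 2% |
| 5% | 30% | 51% | at most 2% |
| 5% | 40% | 71% | at most 2% |
| 5% | 5% | 8% | 2% |
| 10% | 10% | 27% | 8% |
| 15% | 15% | 49% | 16% |

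The last three rows show the cost: stops when the true rate is below the sponsor's own 20% limit.

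**The case against.** The strongest reply is that nobody would apply the literal reading. A limit for the first five followed by a limit thereafter reads naturally as two phases, and it is hard to suppose that a worse grade was meant to be exempt. Section 5.5.11 also introduces the list partly as guidance, with the relationship to VAY736 judged case by case. This stands as to intent, and it is why the point is about wording. It does not remove the ambiguity in a rule that mandates a stop. The neutrophil bullet in the same list writes 'or' where alternatives are meant, and 5.5.7 names grade 4 where grade 4 is meant.

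The second reply is that other safeguards exist, and they do. The opinion clause is in the same mandatory list, the DMC sees unblinded data throughout and reviews every SUSAR, a life-threatening event is an SAE reportable within 24 hours, and a grade 3 or 4 reaction stops that patient's infusion. What each decides about continuing the study is a judgement. The review of the first nine precedes any 10 mg/kg dosing, and the scheduled review that includes 10 mg/kg waits until the 14th patient completes week 12. The DMC charter and the redacted text may hold numeric limits that cannot be seen.

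The third reply is that the cumulative count is only one choice, and that it dilutes a 10 mg/kg signal with 3 mg/kg patients: 3 of 9 reacting at 10 mg/kg (33%) would trigger in only 31% of orders. That is true. A later-only count is more sensitive. Assessed once all 13 later patients are dosed, with 'or', it gives 34%, 60% and 80% at assumed 10 mg/kg rates of 20%, 30% and 40% (5% at 3 mg/kg). Checked after each patient, however, it would stop on a first later reaction (1/1 = 100%). The sponsor should choose and say which count applies.

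**Conclusion.** The point holds as a drafting error in a mandatory safety rule. The logical part needs no assumed rate: with at most one reaction among the first five treated, the literal bullet cannot be met by any number of grade 3 reactions at 10 mg/kg, and a non-fatal grade 4 infusion reaction meets neither toxicity bullet. It rests on taking 'and' and 'grade 3' at their word; the sponsor probably meant successive limits and grade 3 or higher.

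A reader might infer that severe infusion reactions at 10 mg/kg go unchecked, or that the sponsor chose to tolerate them. The documents support neither: the opinion clause, the DMC's unblinded access and the SUSAR reviews are all in place. Nor should 71% against 2% be read as expected performance. It is one point in an assumed range that begins at 14%. Protocol 3.6.2.2.2 reports only mild-to-moderate reactions in rheumatoid arthritis patients at doses up to 10 mg/kg without premedication, and every patient here is premedicated.

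**What to change.** Make three wording changes in Protocol 5.5.11.

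- Infusion-reaction bullet: *More than 1 infusion reaction of grade 3 or higher within the first 5 subjects treated with VAY736, or a cumulative incidence of >20% among VAY736-treated subjects thereafter.*
- General toxicity bullet: change 'grade 3 toxicity' to 'grade 3 or higher toxicity'.
- Vital-sign, ECG and laboratory bullet: change 'and an incidence' to 'or an incidence', and state the same denominator.

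The sponsor's limits of 1 in 5 and 20% stay. The cumulative VAY736 denominator is one reasonable choice: a single later reaction does not stop the study (1/6 = 17%). Whichever count is preferred should be written down.

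The cost is a few words in a protocol amendment, with no change to design, sample size or analysis. The real downside is the higher chance of a precautionary pause when the true rate is below 20%, shown in the last three rows of the table.

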5.5.12 Emergency unblinding of treatment assignment

Emergency unblinding should only be undertaken when it is essential to treat the subject safely and efficaciously. Most often, study drug discontinuation and knowledge of the possible treatment assignments are sufficient to treat a study subject who presents with an emergency condition. A complete set of emergency code break cards will be provided to the investigator site(s) and a complete set will be available at Novartis. All code break cards must be retained until the end of the study and returned to Novartis. They must be stored in a secure place but be accessible in case of emergency. The investigator will receive a blinded code break card for each subject, with the details of drug treatment covered by a removable, scratch-off cover. In an emergency, the scratch-off cover can be removed to determine the treatment. The scratch-off covers are not to be removed for any reason other than an emergency. When the investigator removes the scratch-off cover he/she must note the date, time, and reason for removing it and retain this information with the case report form documentation. **The unblinded treatment code should not be recorded on the CRF.** The investigator must also immediately inform the Novartis local monitor that the code has been broken.

It is the investigator's responsibility to ensure that there is a procedure in place to allow access to the code break cards in case of emergency. If appropriate, the investigator will inform the subject how to contact his/her backup in cases of emergency when he/she is unavailable.

An assessment will be done by the appropriate site personnel and the sponsor after an emergency unblinding to assess whether or not the patient should be withdrawn from the study.

After 24 weeks in the study, at the Week 24 visit (or before in case of early withdrawal from the double-blind period that meets certain conditions – see [Section 5.5.8](#)), patients' treatment will be unblinded. The patient will be informed of the treatment group; if the patient has been treated with placebo, (s)he will be offered the optional open label VAY736 administration.

5.5.13 Study completion and post-study treatment

Each subject is expected to complete the study in its entirety and thereafter no further study treatment will be made available to them. The study will complete when the last subject completes their Study Completion visit, and any repeat assessments associated with this visit have been documented and followed-up appropriately by the Investigator.

The investigator must provide follow-up medical care for all patients who are prematurely withdrawn from the study, or must refer them for appropriate ongoing care.

5.5.13.1 Early study termination

The study can be terminated at any time for any reason by Novartis. Should this be necessary, the patients should be seen as soon as possible and treated as prematurely withdrawn subjects.

Commercially Confidential Information

The investigator may be informed of additional procedures to be followed in order to ensure that adequate consideration is given to the protection of the subject's interests. The investigator will be responsible for informing IRBs and/or ECs of the early termination of the trial.

Should the study be terminated, patients assigned to placebo group will not be offered the optional VAY736 administration.

6 Visit assessments

The full assessment schedule is presented at the end of the synoptic section, above.

Subjects should be seen for all visits on the designated day with an allowed "visit window" of:

- +/- 2 days for Day 8 (Week 1) visit, Day 15 (Week 2) visit
- +/- 3 days for Day 22 (Week 3) visit
- +/- 4 days for Day 43 (Week 6), Day 64 (Week 9), Day 85 (Week 12) visits
- +/- 7 days for Day 113 (Week 16), Day 141 (Week 20), Day 169 (Week 24) visits
- +/- 2 weeks for all additional visits for the safety follow-up period
or up to 2 years after last dose, unless the
patient starts another immunomodulatory or immunosuppressive treatment)

Commercially Confidential
Information

Commercially Confidential Information

The End of Study visit will include study completion evaluations followed by discharge from the study.

Subjects, who discontinue before completing the study, and those who prematurely withdraw from the study for any reason, should be scheduled for a visit as soon as possible, at which time all of the assessments listed for the final visit will be performed.

Deviations for the following assessment times are acceptable based on logistical and operational considerations:

PK sampling

PK samples should be collected as per the assessment visit schedule.

On visit where the treatment is given, PK samples should be collected:

- Pre-dose, before start of the infusion
- At the end of infusion when the line is empty for the 2 h post-dose samples
- 24 h post-dose (start of infusion: +/- 2 h)

ECG, Vital signs

ECG and Vital signs measurements should be performed:

- Up to 2 h pre-dose
- As per the [Assessment schedule](#)

Other samples

- Safety laboratory, blood biomarker should be taken up to 24 h pre-dose.

Every effort will be made to take the pharmacokinetic sample at the protocol specified time. Other assessments e.g. ECG, vital signs etc will be taken prior to / after the pharmacokinetic sample.

Commercially Confidential Information

6.1 Dietary, fluid and other restrictions

On dosing days, patients should not eat for about 1 hour after the end of the infusion. Unless performing a study assessment, patients should rest quietly for the next 2 hours.

Due to the use of Standard of Care adjunct medications it is requested that patients moderate their intake of alcohol and may be required to abstain from alcohol if needed for concomitant medications. No other restrictions are required on the study.

6.2 Subject demographics/other baseline characteristics

Demographics

Subject demographic and baseline characteristic data to be collected on all subjects include: date of birth, age, sex, race, predominant ethnicity.

Relevant Medical history / Current medical conditions

Relevant medical history/current medical conditions data includes data until signature of informed consent. Where possible, diagnoses and not symptoms will be recorded.

PV history and previous PV treatment

Details of the diagnosis, past medical history and previous treatments related to PV and other autoimmune diseases will be collected and entered into the CRF.

Prior and Concomitant Medication/Significant Non-Drug Therapies

All concomitant medications taken or other therapeutic interventions executed within 30 days prior to Screening and during the study must be recorded. Both the start date and the end date for each medication should be captured on the "Concomitant Medications/Significant Non-Drug Therapies" eCRF page.

Hepatitis screen, HIV screen

Patients will be screened for Hepatitis B surface antigen. Screening for Hepatitis C will be based on Hepatitis C virus antibodies.

Evaluation for HIV seropositivity will be performed and, if positive, confirmation by a second technique available at the laboratory site, e.g., Western blot.

The decision whether to re-test patients for hepatitis and HIV should be based on the patient's individual risk and history and should take the duration between completion of the core study and enrollment in the extension study into account.

Results will be available as source data and will not be recorded in the eCRF.

Alcohol test, Drug screen

Subjects will be tested for substances of abuse (e.g., alcohol, amphetamines, barbiturates, benzodiazepines, cannabinoids, cocaine, and opiates). Sample should be sent to central lab for analysis.

Results will be available as Source data and will not be recorded in the eCRF.

Testing for tuberculosis

Testing for tuberculosis will be performed and read at Screening or accepted up to 6 months prior to screening.

Tuberculosis testing should be performed with the QuantiFeron test. Should a study site not have access to the QuantiFeron test, a chest X-ray can be performed instead of the QuantiFeron test.

Chest X-ray: If deemed necessary a standard chest X-ray will be performed. The subject identifier and date of chest X-ray must appear on each film. The report will be dated and signed by the person who makes the interpretation. Historically signed reports will be acceptable, provided the film is archived at the site. The original X-ray film, appropriately labeled, will be archived at study site.

Precaution against tuberculosis should be handled according to the best medical practice consistent to the local standards in each country with prior consultation with Novartis. Patients requiring administration of antibiotics against latent tuberculosis should complete their treatment and should be considered cured prior to being re-considered for entry into this study (consultation with Novartis must occur before allowing the patient to enter the study).

Data will be stored as source data and not collected in the eCRF.

Study completion information

Information on the date the subject last took drug, the subject completion or discontinuation of the study and the reason for discontinuation of the study will be recorded on the Study Completion eCRF page.

Study Completion evaluations must also be performed when a subject prematurely withdraws from the study for whatever reason.

Comments

All comments related to study conduct will be added to the eCRF

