7. History of major organ or hematopoietic stem cell/marrow transplant.
8. Active viral, bacterial or other infections at the time of Screening or Baseline, or history of recurrent clinically significant infection or of recurrent bacterial infections with encapsulated organisms.

9. Evidence of active or latent tuberculosis (TB), or inadequately treated infection with TB, as defined by the following:
 - A positive QuantiFERON® TB-Gold test at Screening or in the 6 months prior to ScreeningOR
 - A chest radiograph positive for active TB infection at Screening or in the 6 months prior to Screening
 - History of either untreated or inadequately treated latent or active TB infection
 - If a patient has previously received an adequate course of therapy for either latent or active TB infection (according to local standard of care or country guidelines), this is to be documented prior to dosing with study drug.
 - Receiving current therapy for active TB infection
 - If receiving treatment for latent TB infection, a patient may not be excluded, and can potentially be recruited but only with prior approval of the sponsor (in consideration of country incidence rates of multi-drug resistant TB, etc.)
10. Recent vaccination with live/attenuated vaccine within a 2 month period prior to Screening.
11. Current signs or symptoms of severe, progressive, or uncontrolled renal, hepatic, hematological, gastrointestinal, endocrine, pulmonary, cardiac, neurologic, cerebral, psychiatric, or other disease which would make the patient unsuitable for the trial.
12. Significant illness within two 2 weeks prior to initial dosing.
13. History of primary or secondary immunodeficiency, including a positive HIV (ELISA and Western blot) test result.
14. Presence of any malignancy of any organ system that has been under active treatment (e.g., radiation therapy or chemotherapy) within the 2 years prior to Baseline or is anticipated to require treatment during the study period (including follow-up) with the exception of patients with removal of uncomplicated basal cell carcinoma or cutaneous squamous cell carcinoma, who may take part in the study.
15. Screening CBC laboratory values as follows:
 - Hemoglobin <10.0 g/dL
 - White blood cell count <3,000/ μ L
 - Platelets <100,000/ μ L
 - Absolute neutrophil count \leq 1,500/ μ L
16. A positive Hepatitis B surface antigen or Hepatitis C test result at Screening.

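### Where a site lacks QuantiFERON, Protocol 6.2 accepts a chest X-ray in its place, leaving no named test at that site for the latent TB that criterion 9 excludes

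*Protocol*

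**What the plan says.** Protocol 4.2, criterion 9, excludes patients with "Evidence of active or latent tuberculosis (TB), or inadequately treated infection with TB, as defined by the following". Four items then trigger the exclusion:

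- the QuantiFERON item, met by a positive result on a "TB-Gold test at Screening or in the 6 months prior", counting back from that visit;
- the radiograph item, worded as "A chest radiograph positive for active TB infection at Screening or in the 6 months prior to Screening";
- the history item, worded as "History of either untreated or inadequately treated latent or active TB infection";
- the therapy item, met by ongoing treatment of active TB.

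Two qualifiers sit under these items. One begins "If a patient has previously received an adequate course of therapy for either latent or active TB infection" and asks for that course to be documented before dosing. The other says that a patient already on treatment for latent TB "can potentially be recruited but only with prior approval of the sponsor".

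Protocol 6.2, under Testing for tuberculosis, says that testing should use QuantiFERON, at Screening or up to 6 months before. It then gives the fallback: "Should a study site not have access to the QuantiFeron test, a chest X-ray can be performed instead of the QuantiFeron test". On radiographs it adds only "If deemed necessary a standard chest X-ray will be performed". The same subsection says that TB precautions should follow good local practice after consulting the sponsor, and that patients who need antibiotics for latent TB should finish them before being reconsidered. TB data are kept as source documents and are not entered in the eCRF.

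The assessment schedule lists a TB assessment at Screening without saying which test.

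**The concern.** The exclusion covers latent infection, but the substitute test, as criterion 9 uses it, can exclude only for active disease. A site that takes the fallback can complete every TB step named in the protocol and still have run nothing aimed at latent infection.

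The stake is patient safety. VAY736 suppresses part of the immune system and is given on top of a corticosteroid, with or without azathioprine or mycophenolate. Protocol 3.6 acknowledges a theoretical increase in infections and the exposure to several immunosuppressants at once. The protocol's arrangements for latent TB (documented earlier therapy, sponsor approval while on treatment, completed treatment before reconsideration) all start from an infection that someone already knows about. An unrecognised case reaches none of them.

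**Working it through.** The plan gives no figure to reproduce, and no probability calculation applies. The check is to set criterion 9 beside the fallback in 6.2 and ask what could identify a patient with undiagnosed latent TB.

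| Criterion 9 item | Test result? | Can it catch unrecognised latent TB? |
|---|---|---|
| Positive QuantiFERON | Yes | Yes: not restricted to active TB |
| Radiograph | Yes | No: must be positive for active TB |
| History of untreated or inadequately treated TB | No | Not without prior knowledge or a separate test |
| Current therapy for active TB | No | No |

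**Step 1.** Of the four items, two are test results. Of those two, one is not restricted to active disease.

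**Step 2.** At a site with QuantiFERON, the number of tests named in the protocol that can trigger the latent-TB exclusion is 1.

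**Step 3.** At a site using the fallback, QuantiFERON is replaced by a film that counts only for active TB: 1 − 1 = 0. This counts what the text names. It does not estimate risk.

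**Step 4.** What is left at such a site:
- a known history, through criterion 9;
- a positive QuantiFERON already on file from the previous 6 months, through criterion 9;
- a latent-TB test done because local standards call for one, through the precaution sentence in 6.2. A positive result in an untreated patient could be read as falling under the history item, or be acted on through the investigator's judgement in criterion 21.

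The third route operates only if the test is done, and the protocol does not name one.

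**Step 5.** Later safeguards. Protocol 6.5.2 watches for signs, symptoms and laboratory results suggesting infection. That may limit the consequences, but it does not find latent infection before dosing. Because TB data stay out of the eCRF, the study database would not show which patients were screened by X-ray alone.

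**Size.** For a patient to be affected, all of these must hold: the site lacks QuantiFERON; the patient has undiagnosed latent TB; the film is not positive for active TB; no positive QuantiFERON is on file from the previous 6 months; and no local test picks it up. The documents give no frequency for any of these, so a number of patients cannot be derived.

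**The case against.** The strongest reply is that 6.2 already covers the case. It says that TB precautions should follow local practice, with the sponsor consulted, and it uses the same verb (should) as the sentence that makes QuantiFERON the default. Where local standards call for latent-TB testing before immunosuppression, the site is directed to follow them. A positive result in an untreated patient could then exclude through the history item. This stands in part. A reader might infer that no latent-TB test would be done at an X-ray site, or that a positive local result could not exclude anyone. The documents support neither. They do show that the protocol names no such test, so screening would vary with local standards.

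A second reply is that the two sections agree: criterion 9 joins QuantiFERON and radiograph with an OR, and 6.2 offers the same two tests as a pragmatic fallback in a very rare disease. The wording is compatible, and the choice may be deliberate. Even so, a radiograph item limited to active TB cannot carry out the latent part of the exclusion.

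A third reply is that the gap is hypothetical and the harm unproven. No document shows a site without QuantiFERON. The visible text does not name TB reactivation as a risk of VAY736, and the risk sections are partly redacted. Latent TB is also not an absolute bar, since a patient under treatment for it may enter with sponsor approval. All of this stands, and it limits the size of the point. It does not remove the mismatch: that approval route is for a known, treated infection, not an unrecognised one.

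**Conclusion.** The point holds in a limited form. If a site lacks QuantiFERON, 6.2 lets a chest X-ray replace it, and the protocol then names no test at that site for the latent TB that criterion 9 excludes. Detection depends on history, a QuantiFERON from the previous 6 months, or local standards. A stated rule can thus defeat a stated exclusion.

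In countable terms, the tests named for latent TB fall from one to zero at an affected site. The number of affected sites is unknown and may be zero, in which case the gap never arises. A reader might go further and infer that patients with latent TB will be enrolled, or that VAY736 reactivates TB. The documents establish neither, and the harm should be put no higher than the general infection risk in Protocol 3.6. The primary analysis is unaffected. The amendment is worth making because the default test is the protocol's own choice and extending it is cheap.

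**What to change.** Amend 6.2 so that a chest X-ray may supplement a latent-TB test but not replace it. A site without QuantiFERON sends the screening sample to a laboratory that runs the assay or, failing that, uses another locally accepted latent-TB test agreed with the sponsor. Add to criterion 9 that a positive result on that test counts, so that exclusion does not rest on a reading of the history item or on criterion 21. This matters because Section 4 tells investigators not to add criteria of their own.

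The text change is two or three sentences. At affected sites it costs one blood tube, shipping and an assay (or a local test) per patient screened, and possibly a few more screen failures. The documents do not show that the central laboratory offers the assay, which is why the wording should allow another laboratory or a local test. If every site has QuantiFERON, the change costs nothing in operation.
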